Chemotherapeutic mouthrinses and toothpastes have been shown to be efficacious in helping to remove the biofilm in conjunction with manual plaque removal with toothbrushing, flossing and oral irrigation.^{4,5} This study investigated the efficacy of an over the counter (OTC) toothpaste and mouthrinse, both produced according to the FDA's CFR21 monograph for products designed to reduce supragingival plaque and gingivitis, for reducing supragingival plaque, gingivitis, and bleeding on probing. The products used in the study were ClōSYS® Sensitive Fluoride Toothpaste, which contains 0.1% stabilized chlorine dioxide (sodium chlorite in an aqueous solution) and 0.13% w/v fluoride ion, and ClōSYS® Sensitive Rinse which contains 0.1% stabilized chlorine dioxide. Early research supports the efficacy of stabilized chlorine dioxide for reducing oral biofilm.⁶ A twice daily oral hygiene regimen using both products was tested in adult subjects diagnosed with gingivitis and early periodontitis.

Objective

The purpose of the study was to evaluate the efficacy of twice daily use of CloSYS Sensitive fluoride toothpaste and Sensitive oral rinse on gingival bleeding upon probing and supragingival plaque in patients with gingivitis or periodontitis (Stage I or II).

Study Design

This was a 90-day, self-controlled, longitudinal, non-blinded clinical trial which measured changes in clinical parameters in participants with gingivitis and Stage I or II periodontitis who applied CloSYS Sensitive fluoride toothpaste twice daily with a toothbrush and CloSYS Sensitive oral rinse twice daily after brushing. Gingivitis was defined as bleeding upon probing with no loss of attachment, and periodontitis was defined when loss of periodontal tissue support through inflammation is the primary feature.

The primary response variables were Subjects' scores on the Plaque Index (PI), Gingival Index (GI) and the number of sites with bleeding upon probing (BOP). Probing depths and clinical attachment level were assessed at baseline and 3 months. Adverse events were assessed and documented at each visit. In addition, Subjects were instructed to keep a usage diary

documenting their daily use of the toothpaste and oral rinse and any comments or observations regarding usage or adverse events.

Number of Subjects

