Subjects were given the right to withdraw from the study at any time and for any reason without prejudice to receiving future dental care at the institution. The PI documented the withdrawal/removal from the study and the reason for withdrawal/removal in the study record. If a subject experienced a complication and wanted to withdraw, if they consented, they were scheduled for an immediate follow-up/closeout examination to determine if an adverse event was present, and if so, the causation of the adverse event was recorded. Every effort was made to follow-up with subjects who withdrew on their own from the study.

Subject data only up to the time when the subjects were withdrawn was kept but was not included in the data analysis of the study.

Off Study

Subjects were considered off study when all planned study visits, early termination, and follow-up visits were completed.

Study Outcomes

This study assessed differences in clinical outcomes at baseline, 6 and 12 weeks. The primary outcomes include changes in gingival and plaque indices (GI and PI, respectively), and bleeding on probing. Because enrolled subjects presented primarily with gingivitis, changes in pocket depth and clinical attachment level were not included in the initial data analysis, as clinically, changes observed were negligible. Secondary outcomes included adverse events, compliance with the oral hygiene regimen and patient product use experience and preferences data.

14. Hypotheses

The hypotheses for the study were as follows:

- Subjects who apply CloSYS Sensitive fluoride toothpaste and Sensitive oral rinse as directed will experience reductions in PI across time.
- Subjects who apply CloSYS Sensitive fluoride Toothpaste and Sensitive oral rinse as directed will experience reductions in GI across time.
- Subjects who apply CloSYS Sensitive fluoride Toothpaste and Sensitive oral rinse as directed will experience reductions in BOP across time.

Statistical Analysis

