Data was coded and entered into an Excel spreadsheet which was then imported into IBM SPSS version 28 for analysis. Descriptive statistics were used to report demographics. The Kruskal-Wallis test, with the Dunn post-hoc test, was used to compare MGI and PI at baseline, 6 weeks and 12 weeks. Pairwise comparisons using Wilcoxon signed rank test was used to compare differences in bleeding on probing (BOP) between baseline and 12 weeks. Adverse events data, compliance data and patient product use experience data were reported using descriptive statistics. All data were de-identified and reported in aggregate form only.

REFERENCES

2. Bosshardt DD. The periodontal pocket: pathogenesis, histopathology and consequences. *Periodontol 2000*. 2018 Feb;76(1):43-50. doi: 10.1111/prd.12153. Epub 2017 Nov 30.
5. Gunsolley JC. Clinical efficacy of antimicrobial mouthrinses. *J Dent*. 2010 Jun;38 Suppl 1:S6-10. doi: 10.1016/S0300-5712(10)70004-X. Review.
8. Löe H. The Gingival Index, the Plaque Index and the Retention Index Systems. *J Periodontol*. 1967 Nov-Dec;38(6):Suppl:610-6.
9. Bessa-Rebelo M, Corrêa de Queiroz, A. Gingival Indices: State of the Art. Available at: https://www.researchgate.net/profile/Maria_Rebelo2/publication/221917002_Gingival_Indices_State_of_Art/links/544658a10cf2f14fb80f32ad/Gingival-Indices-State-of-Art.pdf Accessed January 15, 2020.

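### Three primary outcomes are tested separately with no stated alpha, success rule or adjustment across them: about 14% chance of a false rejection with valid independent tests at an assumed 5%

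*Combined protocol and SAP*

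**What the plan says.** **Primary outcomes.** Study Outcomes states: "The primary outcomes include changes in gingival and plaque indices (GI and PI, respectively), and bleeding on probing". Study Design names the same three as primary response variables. Study Procedures explains that the gingival index is scored with the modified index (MGI).

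**Hypotheses.** Section 14 lists three separate, directional statements, one per index:
- "Subjects who apply CloSYS Sensitive fluoride toothpaste and Sensitive oral rinse as directed will experience reductions in PI across time"
- "Sensitive oral rinse as directed will experience reductions in GI across time"
- "Sensitive oral rinse as directed will experience reductions in BOP across time"

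**Tests.** The Statistical Analysis section uses two methods:
- For gingival index and plaque: "The Kruskal-Wallis test, with the Dunn post-hoc test, was used to compare MGI and PI at baseline, 6 weeks and 12 weeks".
- For bleeding (BOP): "Pairwise comparisons using Wilcoxon signed rank test was used to compare differences in bleeding on probing (BOP) between baseline and 12 weeks".

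**What is absent.** No section gives a significance level, the sidedness of the tests, an order among the three outcomes, a rule for how many must be positive, or an adjustment across them. The Objective refers to effects "on gingival bleeding upon probing and supragingival plaque in patients with gingivitis or periodontitis", so it leaves out the gingival index and supplies no ranking.

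**The concern.** Three hypotheses, each with its own test and all called primary, give three chances at a positive primary result. If one is enough to support a claim, the chance of a false claim somewhere in the set exceeds the level of any single test. The Dunn step does not help, because it compares visits within one index and not the indices with each other.

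A second problem does not depend on any percentage. If one or two of the three outcomes are significant, the plan does not tell the reader whether the study met its primary aim.

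**Working it through.** The document gives no alpha, power or sample-size derivation, so there is no figure of its own to reproduce.

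**Inputs**
- Primary outcomes: 3 (Study Design, Study Outcomes).
- Subjects: 60 in one group, measured repeatedly (Number of Subjects, Study Design).
- Tests: Kruskal-Wallis over three visits for MGI and PI; Wilcoxon signed rank over two visits for BOP (Statistical Analysis).
- Alpha: not stated. Two-sided 5% per test is my assumption.
- Correlations between outcomes and between visits: not stated. Ranges are shown.

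**Step 1. Three valid tests, any rejection**
- Independent: 1 − 0.95³ = 14.3%.
- Upper bound under any dependence: 3 × 0.05 = 15.0%.
- Equally correlated two-sided normal statistics, by simulation: 13.6% at correlation 0.3, 12.5% at 0.5, 10.9% at 0.7.
- Other assumed levels, independent: 1 − 0.99³ = 3.0% and 1 − 0.90³ = 27.1%.

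**Step 2. False reductions only**

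The hypotheses concern reductions, and a two-sided 5% test gives a false reduction 2.5% of the time.
- Independent: 1 − 0.975³ = 7.3%.
- Simulated: 6.9% at correlation 0.3, 6.2% at 0.5, 5.5% at 0.7.
- Comparator for a single test: 2.5%.

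**Step 3. The tests as planned**

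Kruskal-Wallis treats the three visits as independent groups, although they come from the same mouths. With positive correlation between visits it rejects less often than its nominal level. Simulation used 60 subjects, normal data, no change in any index, 4,000 runs per scenario, and between-outcome correlation 0 or 0.5:

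| Assumed correlation between visits | Size of each Kruskal-Wallis test | Any of the three tests rejects |
|---|---|---|
| 0 | about 5% | 13.3% to 14.4% |
| 0.3 | about 1.5% | 7.5% to 7.7% |
| 0.5 | about 0.4% | 5.3% to 5.7% |
| 0.7 | under 0.1% | 5.1% to 5.5% |

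Hand check under independence between outcomes:
- Visit correlation 0.3: 1 − 0.95 × 0.985² = 7.8%.
- Visit correlation 0.5: 1 − 0.95 × 0.996² = 5.8%.

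Nearly all the remaining error comes from the BOP test.

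**Step 4. After the fix**

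With a paired Wilcoxon test for each of the three outcomes, simulation gives roughly 11% to 15% any-rejection without adjustment and about 4% to 5% with Holm. When no index truly changes, Holm's first step compares the smallest p-value with 0.05/3 = 0.0167. The error is then 1 − (1 − 0.0167)³ = 4.9% under independence and at most 5% under any dependence.

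**The case against.** The strongest reply is that 14% does not describe this plan. No 5% level is stated, and the planned Kruskal-Wallis tests are conservative on repeated scores, so the figure for the plan as written is nearer 5% to 8%. That stands. But the low figure comes from using an unpaired test on paired data and is not designed error control. It disappears once MGI and PI are analysed with a valid paired test.

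A reader might infer that the plan lets any one positive test count as success. The document does not say so. Three separate hypotheses permit that reading and nothing rules it out. If all three were required, no adjustment would be needed. If each result were claimed only for its own index, the need to adjust would be debatable. What can be said is that the rule is missing.

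A reader might also infer that there is no multiplicity control at all. That goes too far, because Dunn comparisons follow an omnibus test within MGI and within PI. The gap is across outcomes. Nor does the Objective put the primary set in doubt: Study Design and Study Outcomes agree on it, and only a ranking is missing.

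Finally, this is a single-group before-and-after study in which a prophylaxis followed baseline scoring. All three indices could improve whatever the products do, so error under no change is not the main threat to a product claim. That also stands, and limits the weight of this point.

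**Conclusion.** The gap is real: three primary outcomes, three hypotheses and three tests, with no alpha, no any-versus-all rule and no adjustment across them.

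Its size depends on the tests. With valid paired tests at an assumed two-sided 5%, the chance of at least one false rejection is about 14% under independence, never above 15%, and about 11% to 12.5% at correlations of 0.7 to 0.5. For false reductions alone it is about 5.5% to 7%, against 2.5%. With the tests as planned it is probably about 5% to 8%, if scores at different visits correlate at 0.3 to 0.7. The stronger statement, that the plan as written carries a 14% risk of a false claim, is not supported: it would need a stated 5% level and essentially uncorrelated visits.

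The point should be corrected because the remedy is cheap and the success rule is needed whatever the percentage. It is not the study's largest weakness.

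**What to change.** In the Statistical Analysis section:

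1. State an overall two-sided level of 5%.
2. Define one primary test for each of PI, MGI and BOP: a Wilcoxon signed rank test of Day 90 against Day 0, as already used for BOP. This must be written in, because the section has no such primary test for PI or MGI.
3. Judge the three p-values by Holm's procedure: smallest against 0.05/3 = 0.0167, next against 0.05/2 = 0.025, largest against 0.05, stopping at the first failure. A claim is made only for an outcome that passes.
4. Interpret other visit-pair comparisons for PI and MGI only if that outcome passes.
5. Report adjusted p-values. The text is in the past tense and already comments on observed changes, so label the procedure post hoc if it is added after the data were seen.

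**Cost.** A short rewrite of the analysis paragraph, re-analysis of PI and MGI with a paired test, and slightly larger adjusted p-values. No new data are needed. Holm holds under any correlation between the indices, so none has to be assumed. The change does not make up for the absence of a control group.

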At Visit 3 (90 days), subjects received photos, MGI, PI, PD, CAL, BOP. Remaining products were collected and weighed, with weights recorded on the data collection form. The Diary Usage Form was also collected. The presence/absence of adverse events was assessed and documented. Subjects completed a brief survey about their product use experience and preferences (ease of use, taste, willing to continue regimen, willing to purchase).

The presence or absence of adverse events (yes/no) was documented at each study visit on the data collection form. Adverse events that occurred were described and recorded by the PI on the Adverse Events form. If indicated, photographs were taken and appropriate reporting was made to the ATSU IRB and Study Sponsor according to the study protocol and university policies.

For Visits 2 and 3, compliance was scored as a dichotomous variable (yes/no). Compliance was scored as “yes” if product weights decreased upon return and if self-reported product use according to the study protocol was completed 90% of the time as documented on the returned Diary Usage Form.

At the end of the final study visit, each subject who completed the study in its entirety was given a \$50 Amazon gift card as a reward for successful study completion.

Summary of Study Visits

- Screening exam/Consent
- Visit 1(0 Days) = Baseline
 - ✓ Updated medical history
 - ✓ Photos/Indices (MGI, PI, PD, CAL, BOP)
 - ✓ Dispensed Products
 - ✓ Provided Verbal and Written Oral Hygiene Instructions and Diary
- Prophylaxis provided by dental hygienist
- Visit 2 (45 days)
 - ✓ Updated medical history
 - ✓ Photos/Indices (MGI, PI)

- ✓ Assessed adverse events
- ✓ Collected unused product which was weighed for compliance
- ✓ Collected Diary was reviewed for compliance
- ✓ Dispensed Products and Diary
- Visit 3 (90 days)
 - ✓ Updated medical history
 - ✓ Photos/Indices (MGI, PI, PD, CAL, BOP)
 - ✓ Assessed adverse events
 - ✓ Collected unused product which was weighed and reviewed for compliance
 - ✓ Collected Diary was reviewed for compliance
 - ✓ Subject product use experience and preferences survey completed
 - ✓ Dispensed \$50 gift card reward

Removal of Subjects

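### The set analysed appears to be everyone who did not withdraw, whatever their product use, which is neither the as-directed users in the hypotheses nor all enrolled subjects

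*Combined protocol and SAP*

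**What the plan says.** Section 14, Hypotheses, has three statements of the same form. The one for plaque reads "Subjects who apply CloSYS Sensitive fluoride toothpaste and Sensitive oral rinse as directed will experience reductions in PI across time". The gingival index and bleeding on probing (BOP) follow the same pattern.

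The combined protocol and SAP measures such use. Under Study Procedures, "For Visits 2 and 3, compliance was scored as a dichotomous variable (yes/no"), and a yes is given "if product weights decreased upon return and if self-reported product use according to the study protocol was completed 90% of the time", as shown by the returned diary. Study Outcomes places compliance among the secondary outcomes. Statistical Analysis gives it no further role: "Adverse events data, compliance data and patient product use experience data were reported using descriptive statistics". The Kruskal-Wallis test (Modified Gingival Index, MGI, and plaque) and the signed rank test (BOP) are described without an analysis set.

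Removal of Subjects lets subjects leave freely: "Subjects were given the right to withdraw from the study at any time and for any reason". Their data are then dropped: "Subject data only up to the time when the subjects were withdrawn was kept but was not included in the data analysis of the study". Removal is mentioned only as something to record: "The PI documented the withdrawal/removal from the study and the reason for withdrawal/removal in the study record". No grounds for it are listed.

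**The concern.** Two rules together decide who is tested, and neither was written with the hypotheses in view. Leaving the study takes a subject out altogether. Poor use of the products, in a subject who keeps attending, apparently changes nothing. The result is a set defined by attendance, while the hypotheses are defined by use.

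Two things are at stake. A reported reduction would be read as confirming a statement about as-directed use, although subjects scored non-compliant may have contributed fully to it. And the withdrawal rule discards valid Day 0 and Day 45 plaque and MGI scores. Removal of Subjects itself foresees subjects who want to leave because of a complication, so the discarded data may not be typical of the rest.

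**Working it through.** The plan has no figure to reproduce: Number of Subjects gives 60 without power, effect size, dropout or non-compliance rate. The check sets the rules side by side and then counts heads under assumed rates.

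**Step 1: the rules applied to two subjects.** Suppose both stop the products on Day 50, after attending Visit 2 on Day 45.

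- Use between Visits 2 and 3 is about 5 of 45 days, 5/45 = 11%, well under the 90% diary requirement. Compliance at Visit 3 would be no.
- Subject A attends Day 90. Nothing in Statistical Analysis takes A out, and compliance is descriptive only. A appears to count in full.
- Subject B withdraws. All of B's data are left out, including Day 0 and Day 45 plaque and MGI.

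B's exclusion is explicit. A's inclusion is inferred from the absence of any rule against it.

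**Step 2: what can be recovered for B.** Plaque and MGI are scheduled at Days 0, 45 and 90, so B has two usable visits. BOP is scheduled at Days 0 and 90 only, so B has no second value and could not enter a paired test even if the exclusion rule were lifted.

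**Step 3: head counts.** Let N = 60, taken as the number enrolled (an assumption; the text does not say whether 60 enrolled or 60 completed). Both rates below are assumptions.

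- Analysed = N − withdrawn
- Compliant = analysed − non-compliant attenders (rounded to whole subjects)

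| Assumed withdrawal | Assumed non-compliance among attenders | Enrolled | Analysed | Compliant |
|---|---|---|---|---|
| 0% | 0% | 60 | 60 | 60 |
| 0% | 10% (6) | 60 | 60 | 54 |
| 10% (6) | 0% | 60 | 54 | 54 |
| 10% (6) | 10% (5) | 60 | 54 | 49 |
| 20% (12) | 20% (10) | 60 | 48 | 38 |

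With no withdrawals the analysed set is all enrolled. With no non-compliance it is the as-directed users among those who stayed. Otherwise the three sets differ.

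**Step 4: possible direction.** Set the mean change with as-directed use to 1, and assume that all other subjects (withdrawn or non-compliant) have a fraction e of it.

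- Analysed mean = (compliant + e × non-compliant attenders) / analysed
- All-enrolled mean = (compliant + e × (non-compliant attenders + withdrawn)) / 60

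| Case | e | Analysed mean | All-enrolled mean |
|---|---|---|---|
| 10% / 10% | 0 | 49/54 = 0.91 | 49/60 = 0.82 |
| 10% / 10% | 0.5 | 51.5/54 = 0.95 | 54.5/60 = 0.91 |
| 20% / 20% | 0 | 38/48 = 0.79 | 38/60 = 0.63 |
| 20% / 20% | 0.5 | 43/48 = 0.90 | 49/60 = 0.82 |

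Under these assumptions the analysed mean lies below the as-directed mean and above the all-enrolled mean. If e = 1, for example because the prophylaxis and hygiene instruction given to everyone produce the whole change, all three means equal 1 and the choice of set does not affect the mean.

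**The case against.** The other side has several good points.

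- **Non-compliance is not non-use.** A reader might infer that the tests count people who did not use the products. The documents do not support this. A subject with 85% diary-recorded use, or one who used the products but did not return the diary, does not score yes. The flag is also weak in the other direction, since any fall in product weight meets its weight component.
- **Inclusion of non-compliant attenders is not stated.** A reader might take it as established. It is the natural reading, but removal is mentioned without criteria, so removal for non-compliance cannot be ruled out.
- **The bias does not run one way.** A reader might infer that the analysis simply flatters the products. If the products work, including poor adherers dilutes the effect and is conservative for the as-directed hypotheses. Optimism arises against an all-enrolled target, through the withdrawal rule.
- **A compliance comparison cannot settle attribution.** It is tempting to say that similar change in the compliant and non-compliant groups would show the products did nothing. The groups are self-selected, may differ in brushing and flossing, and the non-compliant group may be very small. No such decision rule is sound here.
- **The larger attribution problem lies elsewhere.** The design is single-arm and unblinded, with a prophylaxis after the baseline measurements. No choice of analysis set cures that.
- **The target is partly a matter of reading.** The phrase about following directions may only describe the regimen, and the Objective does not call for an all-enrolled analysis.

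All of these limit the point. They do not remove it: the withdrawal rule is explicit, the compliance score has no role in the tests, and no analysis set is named.

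**Conclusion.** The mismatch stands and should be corrected. The withdrawal half rests on an explicit sentence. The attending half rests on the absence of any restriction and holds unless undocumented removal criteria were applied.

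The size is unknown, because neither the number withdrawn nor the number non-compliant is given. It is nil if nobody withdrew and all were compliant. At the assumed 10% and 10%, with e between 0 and 0.5, the analysed mean is 0.91 to 0.95 of the as-directed mean, against 0.82 to 0.91 for all enrolled. These figures illustrate the mechanism and do not estimate what happened in this trial. Excluding withdrawals may favour the products and including poor adherers may dilute any effect; the documents do not show which dominates.

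**What to change.** 1. **Primary set.** Replace the exclusion in Removal of Subjects with an analysis of all enrolled subjects who have a baseline. For plaque and MGI, use every available score, including those taken before withdrawal, in a repeated-measures method that accepts incomplete follow-up (for example a mixed model with visit as a factor and subject as a random effect). State the missing-data assumption.
2. **BOP.** Keep the paired analysis of Days 0 and 90. Add a stated sensitivity analysis for missing Day 90 values, for example no change from baseline. Report it as the mean or median change with an interval over all enrolled subjects, because the usual signed rank procedure discards zero differences and would not register the added subjects.
3. **Supportive set.** Repeat the analyses in subjects scored compliant at both Visit 2 and Visit 3, the set that the present hypotheses describe. Show change by compliance status descriptively, with no rule that turns similarity into a conclusion.
4. **Accounting.** Report the numbers enrolled, withdrawn with reasons, removed with the criteria applied, non-compliant at each visit, and analysed for each outcome. Say whether 60 is the number enrolled or completed.
5. **Wording.** State the primary conclusion for subjects instructed to use the regimen. The document is in the past tense and already comments on observed pocket depth and attachment changes, so label this a clarification if it is made after data were seen.

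The cost is modest: the compliance scores were collected and the withdrawn subjects' data were kept, so only analysis work and a few sentences are needed. The estimate may turn out less favourable, and the lack of a comparator remains.

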At the Baseline appointment (Visit 1, Day 0), the Subject had a photograph taken of their mouth. The Gingival Index (GI) was measured first using the Modified Gingival Index (MGI).^{7,8,9} The severity of gingival inflammation was recorded from the buccal, lingual and interproximal aspects of all evaluable teeth as follows:

- Score 0 = absence of inflammation
- Score 1 = mild inflammation or with slight changes in color and texture but not in all portions of the gingival margin or papilla
- Score 2 = mild inflammation, such as the preceding criteria, in all portions of the gingival margin or papilla
- Score 3 = moderate, bright surface inflammation, erythema, edema and/or hypertrophy of the gingival margin or papilla
- Score 4 = severe inflammation: erythema, edema and/or marginal gingival hypertrophy of the unit or spontaneous bleeding, papillary congestion or ulceration

MGIs were determined by visual exam of the gingiva on 4 surfaces for each tooth present except for third molars, for a total of 28 teeth. The total number of teeth exhibiting inflammation affecting all portions of the gingival unit (Score ≥ 2) were noted at each visit. The total number of teeth affected was evaluated for each visit in the final analysis.

Next, the Plaque Index (PI) was recorded on all teeth except for third molars, as originally described by Silness and Löe.^{10,11} The PI was recorded on 4 surfaces of each tooth and scored as follows:

- Score 0 = No plaque in gingival area
- Score 1 = No plaque visible by the unaided eye, but plaque is made visible on the point of the probe after it has been moved across surface at entrance of gingival crevice.
- Score 2 = Gingival area is covered with a thin to moderately thick layer of plaque; deposit is visible to the naked eye
- Score 3 = Heavy accumulation of soft matter, the thickness of which fills out niche produced by gingival margin and tooth surface: interdental area is stuffed with soft debris

To calculate the Plaque Index (PI), the four scores were summed for each tooth, and then all scores for all of the teeth present in a subject's mouth were added to determine a total score. Then, the total score was then divided by the number of surfaces to yield the percentage plaque score used in the final analysis.

Results of the clinical indices were recorded on the approved data collection form by the PI.

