Study products were then dispensed to the subject with both written and verbal instructions for use and the Diary Usage Form. Toothpaste tubes and oral rinse bottles were weighed prior to dispensing, with weights recorded on the data collection form. Dispensed products included two 32-ounce bottles of CloSYS Sensitive oral rinse and two 7-ounce tubes of CloSYS Sensitive fluoride toothpaste and disposable dosing cups. The PI provided both verbal and written oral hygiene instructions as follows:

- Clean between the teeth using dental floss or a proxy brush
- Brush with CloSYS Sensitive fluoride toothpaste for 2 minutes twice daily. Subjects were permitted to brush with either a manual or power toothbrush according to individual preference.
- After brushing, rinse with 15 mL CloSYS Sensitive oral rinse for 30 seconds, then expectorate. Do not eat or drink for 30 minutes after rinsing.

Subjects also received a Diary Usage Form with instructions to complete the form daily. Subjects documented brushing and rinsing behaviors, including the time and date for each brushing/rinsing event. Subjects were also instructed not to use any other oral care products than those given as part of the study during the entire study period. Subjects were instructed to bring back their toothpaste tubes and oral rinse bottles at each subsequent study visit along with the

Diary Usage Form. Self-reported product use and remaining product weight were used to assess compliance with the study regimen.

The subject then received an oral prophylaxis and was scheduled to return in 6 weeks for a follow-up study appointment (Visit 2).

Subjects returned for 2 additional study visits, scheduled every 45 days (Visit 2, Day 45; Visit 3, Day 90).

At Visit 2 (Day 45), subjects received photos and MGI, PI. The presence/absence of adverse events was assessed and documented. The completed Diary Usage Form and remaining products were collected, and products were weighed, with weights recorded on the data collection form. A new Diary form, one new tube of toothpaste, one new bottle of oral rinse and disposable dosing cups were dispensed with instructions to return the form and remaining products at the final study visit (Visit 3).

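### MGI and PI, two of the three primary outcomes, are repeated measures on the same subjects but are compared with tests for independent groups (Kruskal-Wallis, Dunn), while BOP gets a paired test

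*Combined protocol and SAP*

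**What the plan says.** The Study Design section sets out a within-subject comparison: "This was a 90-day, self-controlled, longitudinal, non-blinded clinical trial which measured changes in clinical parameters". MGI and PI are scored at baseline and at both later visits. For the second visit, Study Procedures states "At Visit 2 (Day 45), subjects received photos and MGI, PI", and for the third, "At Visit 3 (90 days), subjects received photos, MGI, PI, PD, CAL, BOP". The Enrollment section gives each subject one identifier that does not change, so the three records can be linked.

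Study Outcomes makes change the primary quantity: "The primary outcomes include changes in gingival and plaque indices (GI and PI, respectively), and bleeding on probing". GI is measured as MGI. The hypotheses are also about change, for example that subjects using the products "as directed will experience reductions in PI across time".

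The Statistical Analysis section then states: "The Kruskal-Wallis test, with the Dunn post-hoc test, was used to compare MGI and PI at baseline, 6 weeks and 12 weeks". The following sentence assigns the Wilcoxon signed-rank test to BOP, baseline against 12 weeks. No section gives a repeated-measures method for MGI or PI, or a reason for treating them differently from BOP.

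**The concern.** Kruskal-Wallis and Dunn's test compare independent samples. Here they would treat 3 × 60 = 180 scores as coming from 180 unrelated people, when there are 60 people each seen three times. The stable difference between a person with much plaque and a person with little stays in the error term. A paired analysis removes it, and removing it is the purpose of a self-controlled design.

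The p-values for two of three primary outcomes therefore do not fit the design. Which way they err depends on what was entered as an observation:

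- **One value per subject per visit, positively correlated over time.** The tests are conservative. Real changes can be missed, above all between adjacent visits.
- **Teeth or surfaces entered as separate observations.** The error could go the other way.

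Study Procedures points to the first. For MGI it refers to a count of affected teeth: "The total number of teeth affected was evaluated for each visit in the final analysis". For PI it describes a total "divided by the number of surfaces to yield the percentage plaque score used in the final analysis". The Statistical Analysis section does not state the unit.

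**Working it through.** **Inputs.** From the documents: 60 subjects, three visits, and the named tests. They give no SD, within-subject correlation, expected effect, alpha or Dunn adjustment, so there is no planned figure to reproduce. Assumed: two-sided 5%; one normally distributed score per subject per visit; equal correlation ρ of 0.3, 0.5 or 0.7 between visits; three pairwise contrasts with Bonferroni adjustment on both sides. Falls are in SD units. Power comes from simulation with 10,000 replicates per cell (Monte Carlo standard error at most 0.5 points).

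**1. Type I error of Kruskal-Wallis.** With N = 180 and n = 60,

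H = [12 / (N(N+1))] × Σ n (R̄_j − (N+1)/2)²

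is referred to chi-square on 2 df. With correlated visits, the contrasts among mean ranks have their variance multiplied by 1 − ρ_s, where ρ_s = (6/π) arcsin(ρ/2) is the rank correlation. Because P(χ²₂ > x) = exp(−x/2), the true error is approximately 0.05^(1/(1−ρ_s)).

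| ρ | ρ_s | 0.05^(1/(1−ρ_s)) | Simulated Kruskal-Wallis | Simulated Friedman |
|---|---|---|---|---|
| 0.3 | 0.288 | 0.05^(1/0.712) = 1.5% | 1.5% | about 5% |
| 0.5 | 0.483 | 0.05^(1/0.517) = 0.3% | 0.4% | about 5% |
| 0.7 | 0.683 | 0.05^(1/0.317) = 0.008% | under 0.1% | about 5% |

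**2. Overall power.** Friedman ranks within each subject: Q = [12n / (k(k+1))] × Σ (r̄_j − (k+1)/2)². With k = 3 and n = 60 this is 60 × Σ (r̄_j − 2)².

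| Pattern (Day 0, 45, 90) | Kruskal-Wallis vs Friedman, ρ = 0.3 | ρ = 0.5 | ρ = 0.7 |
|---|---|---|---|
| Linear: 0, −0.15, −0.3 | 22 vs 30% | 16 vs 39% | 10 vs 61% |
| All by Day 45: 0, −0.3, −0.3 | 30 vs 38% | 25 vs 51% | 19 vs 74% |
| Linear: 0, −0.4, −0.8 | both at least 98% | both at least 98% | both at least 98% |

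**3. Pairwise power.** Dunn divides the difference in mean ranks by √[N(N+1)/12 × 2/n] = √[2715 × 2/60] = √90.5 = 9.51, whatever the correlation. The signed-rank test uses each subject's difference, whose SD is √(2(1−ρ)) = 1.18, 1.00 and 0.77 at ρ = 0.3, 0.5 and 0.7. A 0.3 SD fall is thus 0.25, 0.30 and 0.39 SDs of the difference, so the paired test gains as ρ rises.

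| Contrast | Dunn vs signed rank, ρ = 0.3 | ρ = 0.5 | ρ = 0.7 |
|---|---|---|---|
| Day 0 vs 90, 0.3 SD linear fall | 17 vs 30% | 13 vs 42% | 9 vs 68% |
| Day 0 vs 90, 0.8 SD linear fall | both at least 98% | both at least 98% | both at least 98% |
| Day 45 vs 90, 0.8 SD linear fall | 34 vs 54% | 32 vs 71% | 28 vs 92% |

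**4. Sensitivity to the unit.** This shows only why the unit needs confirming; the documents do not describe tooth-level entry. Suppose 28 teeth per subject were pooled into Kruskal-Wallis, with assumed variance shares of 0.20 for subject and 0.20 for tooth. Type I error under no change would then be 0.7%, 3.0%, 7.3%, 19.2% and 39.1% as the subject-by-visit share goes through 0, 1, 2, 5 and 10% (1,500 replicates each).

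**The case against.** The strongest reply is that, on the unit the document points to, the error is conservative. A significant fall in MGI or PI would not be undermined, and harm arises only where a comparison came out non-significant. The documents report no results, so it is unknown whether that happened. This stands, and it limits how serious the point is.

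Other objections stand in part:

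- **Effect size.** The large power losses belong to a chosen 0.3 SD fall. At 0.8 SD the overall test and the baseline-to-Day-90 contrast lose nothing material. Adjacent-visit contrasts still do, and they bear on whether benefit continues after the first six weeks.
- **Shape of the data.** MGI is a tooth count from 0 to 28, with ties and a possible floor. With an assumed floored count, signed-rank power for Day 0 versus Day 90 at a 0.3 SD fall dropped from 29 to 25% (ρ = 0.3) and from 42 to 35% (ρ = 0.5), against 15% and 12% for Dunn. The gain is smaller but in the same direction.
- **Tooth-level entry.** The figure of up to 39% rests on assumed variance shares for data entry that the documents do not describe. It supports a request to confirm the unit, not a charge of false positives.
- **Adjustment.** The pairwise figures use Bonferroni, whereas Holm is recommended below. Holm never rejects fewer contrasts than Bonferroni, so the signed-rank figures do not overstate the recommended analysis.

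None of this explains why BOP was paired and MGI and PI were not.

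**Conclusion.** The concern holds. The stated tests for MGI and PI do not match a self-controlled design with three visits per subject, and no other provision for pairing is made. The mismatch rests on the text alone; only its size rests on assumptions.

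With one value per subject per visit and correlation 0.3 to 0.7, Kruskal-Wallis runs at 1.5% to under 0.1% instead of 5%. For a linear fall of 0.3 SD, overall power falls short of Friedman by 8 to 51 points (30 − 22 and 61 − 10). For a 0.8 SD fall the loss is confined to adjacent-visit contrasts. A significant result is safe from this particular error; a non-significant one is not evidence of no change. If the unit was the tooth or surface, that reassurance does not apply.

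This should be fixed, but it is not shown to overturn any result.

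**What to change.** For MGI and PI:

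1. State the unit of analysis, the alpha level, and the adjustment used with Dunn.
2. Replace Kruskal-Wallis with Friedman on one value per subject per visit.
3. Replace Dunn with paired Wilcoxon signed-rank contrasts for the three visit pairs, Holm-adjusted. Holm controls the error rate across the three by itself, so they need not wait for a significant Friedman test.
4. Report within-subject change from baseline with a 95% confidence interval at Day 45 and Day 90, naming the interval method (Hodges-Lehmann would match the signed-rank test). This is the quantity Study Outcomes calls primary.
5. Present this as a corrected re-analysis beside the Kruskal-Wallis results, labelled as post hoc.

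The cost is small and no new data are needed. Friedman requires all three visits. Removal of Subjects already leaves withdrawn subjects out, but someone who stayed in and missed Visit 2 would drop out of Friedman. If there are such subjects, a mixed model or GEE that accounts for repeated measures on each subject would use their data. If the correlation were in fact zero, Friedman would be the weaker overall test (22 against 28% for a 0.3 SD linear fall), while the signed-rank Day 0 versus Day 90 contrast would lose about one point (20 against 21%).

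The change does not supply a control group, nor does it separate the products from the prophylaxis given at the baseline visit.
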